Asthma has been identified as the most common chronic disease in early childhood and it places a higher burden on minority groups and the poor. Children ages 0-4 years have been identified as the driving force behind increased rates of hospitalization for children with asthma. Furthermore, black children are approximately 2.5 times likely to have an ED visit or hospitalization than white children. Reflecting this increased risk, the prevalence of asthma among low-income preschool children attending Head Start programs is high, ranging from 14% to 35%. For these reasons, asthma has been identified as a key health risk for Head Start children by the Department of Health and Human Services and the Environmental Protection Agency. Thus, Head Start programs offer a timely and important venue for reaching high-risk, low-income pre-school children and providing asthma education interventions. We therefore propose to draw on our established health and research partnership with Head Start programs in Baltimore City to test the effectiveness of a home-based asthma education intervention (ABC) with demonstrated efficacy. Specifically, we will conduct a randomized clinical trial of a culturally-tailored home-based asthma education intervention combined with a HS-level asthma education program in reducing asthma morbidity among low income minority children compared to a HS-level asthma education program alone. We will enroll 406 HS students aged 2-6 years with caregiver-reported symptomatic asthma from all 16 Baltimore City HS programs. The primary study outcome measure will be symptom free days at six month follow-up. Secondary outcomes include caregiver-reported healthcare utilization for urgent (ED visits and hospitalizations) and non-urgent (primary and specialist care) asthma visits, caregiver-reported oral steroid bursts, caregiver-reported asthma control and caregiver quality of life. In addition, at the HS level, we will assess overall HS participation in the HS-level asthma education program and any additional programs or institutional changes that would indicate adoption, implementation and maintenance of asthma education as a core HS health goal and changes in HS staff knowledge, attitudes and practices related to asthma management.

JHMIRB eFormA 01
Version 3 Dated: 06/2007

Page 2 of 13

Date: January 26, 2017

Principal Investigator: [name].

Application Number: NA_00046455

2. Objectives (include all primary and secondary objectives)

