Primary Objectives: Assess the relative effectiveness of the ABC intervention combined with Head Start (HS)-level asthma education (ABC group) in improving asthma morbidity compared to HS-level asthma education alone (Control group) in preschool children with symptomatic asthma. Primary Hypothesis (#1): Participants receiving the ABC intervention will have more symptom free days at the 6-, 9-, and 12-month evaluations when compared with participants in the control group. (#2): Participants receiving the ABC intervention will have reduced morbidity, including decreased urgent care utilization (hospitalizations/ED visits measured by caregiver report as well as insurance payer data), improved quality of life, improved asthma control, and fewer courses of oral steroids, when compared with participants in the Control group at the 6-, 9-, and 12-month evaluations.

Secondary Objectives: Assess the degree to which HS program-level adoption, implementation and maintenance of asthma education activities (stratified as high implementation vs. low implementation) moderates the impact of child-level treatment assignment (ABC vs. Control) on measures of asthma morbidity, including symptom-free days, urgent care, quality of life, asthma control and oral steroids.

Secondary Hypothesis (#3): Participants receiving the ABC home-based intervention combined with high implementation of HS-level asthma education will have reduced asthma morbidity, including decreased urgent care utilization, improved quality of life, improved asthma control, and fewer courses of oral steroids, when compared with participants receiving the ABC intervention in low implementation of HS-level asthma education, or Control group participants at the 6-, 9-, and 12month evaluations. The secondary outcome measures include other measures of asthma morbidity (i.e., ED visits and hospitalizations, oral steroid bursts, asthma control and caregiver quality of life).

3. Background (briefly describe pre-clinical and clinical data, current experience with procedures, drug or device, and any other relevant information to justify the research)

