This study is designed to evaluate the effectiveness of a home-based asthma education intervention (ABC) with demonstrated efficacy in combination with a Head Start level intervention (ABC + HS) to improve asthma morbidity compared to a Head Start level intervention (HS Only) containing asthma education implemented in the Head Start Programs. The study design is a two group randomized clinical trial (N=406). Participants will be children with symptomatic asthma enrolled in Baltimore City Head Start Program Sites (age 2-6) and their families. Participants will be recruited from Head Start and randomly assigned to ABC combined with HS asthma education or HS asthma education alone. The ABC intervention is home- asthma education intervention that was tailored, based on our prior research and that of others, to reflect known cultural barriers to effective asthma management among low-income minority families, including underutilization of asthma primary care, overestimation of asthma control, perceptions that asthma is an episodic illness that only needs acute treatment, negative beliefs about controller medications, and environmental risk factors in the home. All intervention visits will be audio-taped. Outcome measures will be collected at 3-, 6-, 9- and 12-months. The primary outcome measure will be symptom free days at six month follow-up. Secondary outcome measures include other measures of asthma morbidity (i.e., ED visits and hospitalizations, oral steroid bursts, asthma control, and caregiver quality of life). In addition, at the Head Start level, we will evaluate over five years the overall HS participation in the HS-level asthma education program and any additional programs or institutional changes that would indicate adoption, implementation and maintenance of asthma education as a core HS health goal and changes in HS staff knowledge, attitudes and practices related to asthma management.

Staff Safety

In order to assure safety for our study team we do the following: (1) All of our study team members are provided with a cell phone to be kept with them at all times. (2) We conduct annual safety training with a member of the police department. (3) We request that our study team members not conduct home visits at night. (4) All study team members are encouraged to request a second team member attend any home visit that makes them feel uncomfortable.

Screening

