Asthma Outreach workers: Interested Asthma Outreach Workers will have the study described to them in detail by a JHARC study team member on an individual basis. Asthma Outreach Workers will be told about the study, given an opportunity to ask questions about participation and informed that participation is voluntary and has no effect on their employment status at Johns Hopkins University. Staff participation consists of Asthma training by JHARC staff and a brief knowledge and satisfaction survey pre and post training.

Randomization

Randomization will occur after baseline data collection and the group assignment will be recorded. Children will be individually randomized to either the ABC + HS intervention or HS intervention alone. Blocked randomization will be used so that staff cannot predict which treatment will follow. We will stratify randomization by Head Start program to control for clustering within Head Start programs.

Baseline and Follow-up Assessments

Baseline measures will be collected prior to intervention delivery. The baseline assessment consists of an environmental home assessment, skills checklist, weight and height of the child and a survey, will be completed in the family's home by a research assistant (RA) before randomization. Families who are unable to locate their spacer or state they do not have a spacer, will be provided one at this time. Participants will receive \$50 for completing this home visit.

Follow-up assessments will be completed 3-, 9-, and 12- months and will consist of a survey that will be completed over the phone. Participants will receive \$30 for completing these phone visits. 6-month followup assessments will be conducted in the home and consist of an environmental home assessment, skills checklist, weight and height of the child and a survey. Participants will receive \$50 for completing this home visit.

Current Medication Treatment Plan (CMTP)

A CMTP for each participant will be obtained from the child's asthma care providers at Baseline and 12 month follow-up visits. The CMTP will contain information about start and end dates for asthma medications as well as drug name, dose and prescribed frequency.

Pharmacy Refill History

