Medication refill data will be obtained by faxing all family-identified pharmacies and their pharmacy benefits managers or insurance payer. We will get the refill records for one year before joining the study and following their 12 month phone survey (or 12 months after randomization if the 12 month visit is not completed).

Date: January 26, 2017

Principal Investigator: [name].

Application Number: NA_00046455

Health Outcome data

When available, healthcare utilization data will be obtained from insurance payers to validate caregiver report of utilization. This information includes: hospitalizations, ED visits, and PCP visits.

Head Start Staff Assessments

Prior to the delivery of the HS-level asthma education program at a HS program, all staff members (Family Service Coordinators, Teachers, Administrators) at HS centers (N=500) will be asked to complete a survey about knowledge, attitudes and practices related to asthma management. The survey will also include questions about personal knowledge about asthma management and Head Start policies about asthma management, their own health beliefs about asthma management, asthma beliefs about barriers to asthma management, and how often they engage in professional activities related to asthma management either directly with the children or indirectly in parent or staff trainings. The questionnaire will explicitly indicate that survey data will be maintained without personal identifiers and that completion of the survey indicated consent. Staff members who complete and return the survey will receive \$10 compensation each year. This survey will also be completed immediately prior to initiation of the HS asthma educational staff workshops and materials distribution and in years 2 and 5. Staff may return the survey to a locked box at the site or by mail (envelope provided). Surveys will be distributed a second time to nonresponders.

Intervention

We propose to conduct a randomized controlled trial of a home-based asthma education intervention for Head Start students, nested within the context of a HS-level asthma education program. We will partner with Baltimore City Head Start to assist them in implementing this HS-level asthma education program across all Head Start programs. We describe below the randomized trial and our role in the HS-level asthma education program.

Control Condition (CC).

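### Hypothesis #3 does not match its Secondary Objective: the Objective asks whether implementation moderates the ABC effect, but neither comparison the hypothesis names measures that, and no interaction analysis is specified

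*Combined protocol and SAP*

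**What the plan says.** **Objective.** In section 2 (Objectives), the Secondary Objective is to assess how far program-level adoption, implementation and maintenance "moderates the impact of child-level treatment assignment (ABC vs. Control) on measures of asthma morbidity". The moderator is "stratified as high implementation vs. low implementation". No cut-off, score or classification date is given.

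**Hypothesis.** Secondary Hypothesis #3, directly below, predicts reduced morbidity for ABC children in high-implementation programs "when compared with participants receiving the ABC intervention in low implementation of HS-level asthma education, or Control group participants". The Control comparator is not split by implementation. The hypothesis lists urgent care, quality of life, asthma control and oral steroids. The Objective also lists symptom-free days.

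**Design.** Section 4 (Randomization) states: "Children will be individually randomized to either the ABC + HS intervention or HS intervention alone", and "We will stratify randomization by Head Start program to control for clustering within Head Start programs". Implementation is not assigned. Under Intervention, the investigators will work with Baltimore City Head Start to "assist them in implementing this HS-level asthma education program across all Head Start programs". The opening summary gives the number of programs: "We will enroll 406 HS students aged 2-6 years with caregiver-reported symptomatic asthma from all 16 Baltimore City HS programs".

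**Analysis.** Study Statistics, item c, has no arm-by-implementation term and no power for Hypothesis #3. Program enters the models only if the observed intraclass correlations (ICCs) point to clustering.

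**The concern.** Moderation of a randomised effect is a difference of differences: ABC minus Control in high-implementation programs, less ABC minus Control in low-implementation programs. Hypothesis #3 names neither that quantity nor its parts.

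Programs that implement more may differ from those that implement less in case mix, in staffing, or in what the Head Start education itself achieves. Any such difference affects ABC children in high and low programs whether or not ABC works better in one type. An analyst who followed the hypothesis as written could report that implementation enhances ABC when the ABC effect is the same everywhere. The reverse error is also possible: a program difference in the opposite direction could hide a real interaction.

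**Working it through.** **Inputs from the documents.** 16 programs; 346 children analysed, about 173 per arm; SD 6.85 for symptom-free days; within-subject correlation rho 0.5-0.7 (Study Statistics, item c; program count from the opening summary).

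**Assumptions.** Two-sided alpha 0.05 (not stated); high/low split of 8/8 or 4/12 programs of similar size; ICC 0-0.10; ABC effect 2.5 days in the simulation; no variation in the ABC effect between programs of the same type. Symptom-free days are used because this is the only outcome with an SD.

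**The plan's own figure.** There is none for Hypothesis #3. The analysed sample follows from attrition: 406 x 0.85 = 345, against 346 stated. Table 1 concerns the main effect only. It does not reproduce from 23% of 23.65 = 5.44 days: standard two-group variants give a total N of about 20-68 for 90% power, against 248-346. The model behind Table 1 is not given in full, and nothing below depends on it.

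**What each comparison estimates.** Let A be the ABC effect in low programs, I the extra ABC effect in high programs, and G the high-low difference among children without ABC.
- ABC-high minus ABC-low = (A + I + G) - A = I + G.
- ABC-high minus all Controls (even split) = (A + I + G) - G/2 = A + I + G/2.
- Difference of differences = [(A + I + G) - G] - [A - 0] = I.

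Only the third isolates I. Randomisation stratified by program is meant to put both arms in every program, so I can be estimated.

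**Consequence when I = 0.** SE of ABC-high versus ABC-low, unadjusted, ICC 0: 6.85 x sqrt(2/86.5) = 1.04 days. With G = 2, the chance of a significant result favouring the hypothesis is Phi(2/1.04 - 1.96), about 48%. Simulation (3,000 trials per scenario, 8/8 programs, ICC 0 to 0.05), share significant in favour of Hypothesis #3:

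| G (days) | ABC-high vs ABC-low, child level | ABC-high vs ABC-low, program level | Difference of differences |
|---|---|---|---|
| 0 | 2-5% | 2-3% | 2-3% |
| 2 | 48% | 30-44% | 2-3% |
| 3 | 77-83% | 57-77% | 2-3% |

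The nominal rate in one direction is 2.5%. Allowing for clustering lowers the error but does not remove it, because G is bias, not only variance.

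For ABC-high against all Controls with I = 0 and G = 0: SE = 6.85 x sqrt(1/86.5 + 1/173) = 0.90, and Phi(2.5/0.90 - 1.96) is about 79% (simulation 76-79%). That is the main effect showing through.

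**Precision of the right quantity.**
- Main effect: SE = 6.85 x sqrt(4/346) = 0.74 days.
- Interaction, 8/8: SE = 6.85 x sqrt(4/173 + 4/173) = 1.47. Detectable at 80% power: 2.80 x 1.473 = 4.1 days.
- With baseline adjustment, multiply by sqrt(1 - rho^2): 4.13 x 0.866 = 3.6 days at rho 0.5; 4.13 x 0.714 = 2.95 days at rho 0.7.
- Interaction, 4/12, unadjusted: SE = 6.85 x sqrt(4/86.5 + 4/259.5) = 1.70. Detectable: 4.8 days.
- Unadjusted power for an interaction of 2, 2.5 or 3 days: 27%, 40%, 53% (8/8); 22%, 31%, 42% (4/12).

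**If program were ignored.** Design effect = 1 + (173/16 - 1) x ICC. At ICC 0.02, 0.05 and 0.10 this is 1.20, 1.49 and 1.98. Two-sided type I error for ABC-high versus ABC-low, 2 x [1 - Phi(1.96/sqrt(design effect))], is 7.3%, 10.8% and 16.4%.

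**The case against.** **A hypothesis is a prediction, not an analysis.** Nowhere do the documents say that moderation will be tested by ABC-high versus ABC-low, and the Objective already states the right target. This stands. A reader might infer that the plan has committed itself to the wrong test, but the text supports less: the hypothesis does not match its objective, and no analysis fills the gap.

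**The bias figures are for unadjusted follow-up scores.** Symptom-free days are measured at baseline. If the high-low difference is stable and already present then, a change-score analysis would remove all of an assumed 2 days. Baseline adjustment would leave 2 x (1 - rho) = 0.6 to 1.0 day at rho 0.7 to 0.5. The plan does not say which model it will use. A program difference that arises after baseline, for example from the Head Start education itself, would remain. So a reader should not infer that program differences always pass through in full.

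**Clustering is not simply ignored.** Study Statistics plans nested models when ICCs suggest an effect. If that meant an F-test at 5% on 16 equal programs (an assumption), it would flag clustering about 29%, 68% and 94% of the time at ICC 0.02, 0.05 and 0.10. The 16% error rate is therefore the case the plan is most likely to catch. The provision does not remove the bias in the contrast.

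**Timing of the moderator.** The Study design text says "we will evaluate over five years the overall HS participation in the HS-level asthma education program", while each child is followed for 12 months. A reader might infer that children will be classed by activity after their own outcome. No section says that the five-year record will be used for classification, so this is an open definition, not a demonstrated error.

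**Outcome used.** The figures are for symptom-free days, which Hypothesis #3 does not list. They do not carry over to visit or steroid counts, where interaction depends on the scale.

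**Conclusion.** The point holds as a mismatch between the Secondary Objective and Hypothesis #3, with no interaction analysis to bridge it. Neither named comparison estimates moderation: one adds any high-low program difference to the interaction, and the other mostly carries the ABC main effect. The algebra needs no assumed values. The sizes do: the 48% false-support rate needs a 2-day program difference, an even split and no baseline adjustment, and the 7-16% type I error applies only if program is left out.

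The interaction can be estimated, but weakly: about 4.1 days detectable at 80% power unadjusted, about 3.0-3.6 with baseline adjustment, and about 4.8 unadjusted with a 4/12 split. Study Statistics describes improvements of 2-3 days a month as clinically meaningful.

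Two stronger conclusions should not be drawn. The primary ABC-versus-Control comparison is unaffected, since children are randomised individually within program. And a significant interaction would not show that implementation causes a change in the ABC effect, because implementation is not randomised. It would show that the effect differs between program types.

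**What to change.** - Restate Hypothesis #3 as a test of the arm-by-implementation interaction. Keep Head Start program in the model in all cases, not only when the ICC suggests it, and adjust for baseline where the outcome has a baseline value.
- Report ABC minus Control within high and within low programs, with confidence intervals. Treat ABC-high versus ABC-low as descriptive.
- Define high and low implementation before outcomes are seen, using implementation data that precede the child's outcome where such data exist.
- State the scale of the interaction for count outcomes, and make the outcome lists of the Objective and Hypothesis #3 agree on symptom-free days.
- Label the test exploratory, give its detectable size, and say that it compares program types and does not establish that implementation is the cause.

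**Cost.** Mostly wording in Objectives and Study Statistics, with no change to randomisation or child follow-up. The interaction is less precise than the simple contrast (SE 1.47 against 1.04 days, unadjusted, even split, ICC 0). Dated implementation data may need collection that is not now planned: Head Start Staff Assessments places the staff survey before the program and in years 2 and 5, and no section describes yearly scoring of each program.

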Secondary outcomes include caregiver-reported healthcare utilization for urgent (ED visits and hospitalizations) and non-urgent (primary and specialist care) asthma visits, caregiver-reported oral steroid bursts, caregiver-reported asthma control and caregiver quality of life. We will also collect objective data on healthcare utilization from insurance payers to validate caregiver report. In addition, at the HS level, we will assess overall HS participation in the HS-level asthma education program and any additional programs or institutional changes that would indicate adoption, implementation and maintenance of asthma education as a core HS health goal and changes in HS staff knowledge, attitudes and practices related to asthma management.

- c. Statistical plan including sample size justification and interim data analysis.

The power analysis is based on differences in symptom free days between the ABC group and the control group. We expect to recruit 406 total families (203 each group) and anticipate up to 15% of those enrolled will be lost to follow-up for a final sample of 346 families included in the analyses. We chose this sample size because under a variety of scenarios, discussed below, it is considered sufficient to detect a similar increase in symptom free days seen in our previous study. Symptom free days will be assessed at baseline, 3-, 6-, 9- and 12-months postrandomization. Choices for treatment effects, variability, associations (to account for the longitudinal nature of the study), and loss to follow up rates were informed by our previous

Date: January 26, 2017

Principal Investigator: [name].

Application Number: NA_00046455

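### Hypothesis #3 does not test the moderation question set by its own Secondary Objective, so a plain ABC effect could be read as proof that Head Start implementation matters

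*Combined protocol and SAP*

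**What the plan says.** Section 2 (Objectives) of the combined protocol and SAP sets a Secondary Objective of moderation: whether program-level implementation, "stratified as high implementation vs. low implementation", "moderates the impact of child-level treatment assignment (ABC vs. Control) on measures of asthma morbidity". The outcomes named there are symptom-free days, urgent care, quality of life, asthma control and oral steroids.

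The matching hypothesis makes a directional prediction: "Secondary Hypothesis (#3): Participants receiving the ABC home-based intervention combined with high implementation of HS-level asthma education will have reduced asthma morbidity". It lists four outcomes, omitting symptom-free days. The comparison groups are children receiving "ABC intervention in low implementation of HS-level asthma education, or Control group participants at the 6-, 9-, and 12month evaluations".

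On the analysis, the Study Statistics section (item c) says "The power analysis is based on differences in symptom free days between the ABC group and the control group". It names intention-to-treat, weighted GEE or likelihood methods, sensitivity analyses for missing data, and nested models if the ICC shows clustering by program. It gives no interaction term, no cut-point between high and low implementation, no significance level and no rule for when Hypothesis #3 is supported. Section 4 (Randomization) says that children are randomised individually, stratified by Head Start program.

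**The concern.** Moderation means that the ABC-Control difference is larger in one kind of program than in the other. Four groups are needed to see it: ABC and Control in high-implementation programs, and ABC and Control in low-implementation programs. Hypothesis #3 drops part of this in each comparison.

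- **ABC-high versus Control.** If ABC works equally well everywhere, ABC-high children do better than Control children. The comparison succeeds although implementation makes no difference.
- **ABC-high versus ABC-low.** High and low implementation are not assigned at random. Programs that implement well may differ in families, staff or background asthma burden. Without the Control children from the same programs, such a difference cannot be separated from a change in the ABC effect.

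At stake is the conclusion that Head Start implementation enhances ABC. That conclusion would guide how programs are run, and it could be drawn from data showing only that ABC works, or only that programs differ.

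**Working it through.** **Inputs from the documents.** 406 families, 203 per arm; up to 15% lost; 346 analysed; 16 programs; within-subject correlation 0.5 to 0.7 (Table 1).

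**Assumptions, because the documents are silent.** Two-sided 0.05 per test; ABC children split evenly between high and low implementation; ABC effect 0.2 to 0.35 SD, equal in all programs; between-outcome correlation 0 to 0.7.

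**The plan's own figure.** The plan gives no power or error rate for Hypothesis #3. Its analysed number is consistent with its dropout rate: 406 × 0.85 = 345.1, against 346 stated. Hence 173 per arm and 173/2 = 86.5 in each half of an arm.

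**Step 1. What each contrast estimates.** Let τ be the ABC effect in low-implementation programs, γ the extra ABC effect under high implementation (the moderation), and β the difference between high and low programs that is present regardless of arm. With an even split, Control children pooled over programs average β/2.

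| Contrast | Expected value | Value if γ = 0 |
|---|---|---|
| ABC-high − all Control | τ + γ + β/2 | τ + β/2 |
| ABC-high − ABC-low | γ + β | β |
| (ABC − Control in high) − (ABC − Control in low) | γ | 0 |

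Only the third is zero whenever there is no moderation.

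**Step 2. ABC-high versus Control with no moderation (γ = 0, β = 0).**

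SE = √(1/86.5 + 1/173) = 0.1317 SD.

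- Effect 0.20: 0.20/0.1317 = 1.519; Φ(1.519 − 1.96) = 0.33.
- Effect 0.35: 0.35/0.1317 = 2.658; Φ(2.658 − 1.96) = 0.76.

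So one such test is significant in favour of ABC-high in 33% to 76% of trials, when the correct answer to the moderation question is no.

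**Step 3. ABC-high versus ABC-low with clustering ignored.** With 173 ABC children in 16 programs, the average is 10.8 per program. Design effect = 1 + (10.8 − 1) × ICC. For an assumed ICC of 0.01, 0.02 and 0.05 this is 1.098, 1.196 and 1.491. The true size of a nominal 5% test is 2 × [1 − Φ(1.96/√DE)] = 6.1%, 7.3% and 10.8%. The conditional nested model in the plan would address this inflation. It would not remove a systematic difference β between the two groups of programs.

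**Step 4. If any cell counted.** 4 outcomes × 3 visits × 2 comparators = 24 cells. The two comparators share the ABC-high group, so their correlation is (1/86.5)/√[(1/86.5 + 1/86.5)(1/86.5 + 1/173)] = 0.58. Simulation from a 24-dimensional normal with that correlation, counting only results in favour of ABC-high:

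| Setting | At least one favourable cell |
|---|---|
| No ABC effect; outcome correlation 0 to 0.7, visit correlation 0.5 to 0.7 | 21% to 36% |
| ABC effect 0.2 to 0.35 SD on every outcome, no moderation; outcome correlation 0.3 to 0.7, visit correlation 0.5 to 0.7 | 75% to 99.9% |

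**Step 5. Price of the correct contrast.** With four groups of 86.5, the interaction has SE = √(4/86.5) = 0.2150 SD. That is 0.2150/0.1317 = 1.63 times the SE against Control, and 0.2150/0.1521 = 1.41 times the SE against ABC-low, where √(2/86.5) = 0.1521.

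**The case against.** The best defence is that the Secondary Objective itself uses the language of moderation, and the planned GEE or likelihood models could carry an interaction term. An analyst might well fit one. That is fair, but the hypothesis is the only place where the comparison is spelled out, and it spells out two pairwise contrasts. Nothing in the Study Statistics section replaces them.

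A second defence concerns multiplicity, and much of it stands. A reader might infer that the plan lets one significant cell confirm the hypothesis, that it has no hierarchy, and that a false claim is therefore more likely than not. The documents do not support this.

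- No sentence says that one cell is enough. Outcomes and visits are joined by 'and'; only the comparators are joined by 'or'. If the same cell had to beat both comparators, the chance under no ABC effect would be about 4% to 6%. If all 12 cells against ABC-low had to be significant, it would be about zero.
- There is a hierarchy above this hypothesis: it is labelled secondary, and the plan states that "The primary outcome measure will be symptom free days at six month follow-up". Only an order within the hypothesis is missing.
- The hypothesis is directional. Counting results in either direction gives 42% to 62% for any cell under no ABC effect, but that includes results against ABC-high, which could not support it. The relevant range is 21% to 36%, and even 24 independent tests give 1 − 0.975^24 = 45.5%.
- A longitudinal model could pool the three visits, and the plan allows for nested models if clustering is seen.

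None of this meets the main point. The wrong contrast remains wrong with one outcome, one visit and perfect error control.

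**Conclusion.** The concern holds as a mismatch between objective and hypothesis. As written, Hypothesis #3 could appear supported when implementation does not change the ABC effect. For a single ABC-high versus Control test the size is 33% to 76%, resting on an assumed uniform ABC effect of 0.2 to 0.35 SD, two-sided 0.05 and an even split. An uneven split would change these figures but not the reasoning in Step 1. The any-cell figure of 21% to 36% is conditional on a success rule that the plan neither states nor excludes, so it is a supporting point only. The issue concerns a secondary hypothesis and leaves the primary comparison of ABC with Control untouched.

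**What to change.** In section 2, restate Hypothesis #3 as a treatment-by-implementation interaction: the difference in the ABC-Control effect between high- and low-implementation programs. Make symptom free days at 6 months the lead outcome. It is already the primary outcome, and the Secondary Objective names symptom-free days although the hypothesis omits them. Remove the comparison with Control participants as a route to support.

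In Study Statistics item c, add the interaction term to the GEE or likelihood model, with Head Start program accounted for, and state how high and low implementation are defined before outcome data are examined. Report the other outcomes and visits as interaction estimates with 95% confidence intervals.

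Randomisation within program means that both arms should be represented in high- and low-implementation programs, so no new data and no change in sample size are needed. The cost is precision: the standard error is 1.41 to 1.63 times that of the pairwise contrasts (Step 5), before any allowance for having only 16 programs, so a claim of moderation is harder to reach. Because implementation is not randomised, even a clear interaction would show that the ABC effect differs between kinds of program, not that implementation caused the difference. The text should say so.
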